9.8.3. Laboratory Data

Clinical laboratory values will be evaluated by subject for each laboratory parameter at Weeks 2, 6, 12, 24, 36, 52, early termination and safety follow-up. Laboratory test results will be reported and they will be assigned a LNH classification by each laboratory according to whether the value was below (L), within (N), or above (H) the laboratory reference range. Reference (normal) ranges for laboratory parameters provided by the central lab will be included in the clinical study report for this study and will be used for shift tables. Summary tabulations of the continuous clinical laboratory (hematology, chemistry, thyroid function (TSH, free T3 and free T4), and urinalysis) data (n, mean, standard deviation, median, minimum, and maximum) for baseline, each scheduled visit (defined in [Table 1](#)), and change from baseline for laboratory data will be provided. Quantitative urinalysis data will only be listed. Shifts from baseline to each scheduled visit will be summarized for hematology, chemistry, thyroid, and urinalysis variables that are assigned a LNH classification. In addition, shifts from baseline to worst post-baseline for the same laboratory variables will be presented based on the LNH classification.

Prespecified continuous laboratory hematology (WBC, Neutrophils, Lymphocytes) and chemistry (AST, ALT, GGT, Glucose, CK) parameters will have the worst post-baseline value plotted versus the baseline visit. The minimum lower limit of the normal range and the maximum upper limit of the normal range amongst laboratories will be drawn on the x and y axis as vertical lines.

All laboratory data collected will be included in the data listings.

9.8.4. Systolic and Diastolic Blood Pressure and Pulse Rate

Systolic and diastolic blood pressure and pulse rate will be measured in both the supine and standing positions. The scheduled visits that will be summarized are Weeks 2, 6, 12, 24, 36, 52, early termination and safety follow-up.

Summary tabulations of the systolic and diastolic blood pressure and pulse rate in both standing and supine positions as well as the orthostatic change (n, mean, standard deviation, median, minimum, and maximum) for each scheduled visit, and change from baseline will be provided.

At each scheduled visit and time point (Weeks 2, 6, 12, 24, 36, 52, early termination and safety follow-up), the number and percent of subjects meeting each abnormal criteria displayed below will be summarized.

- Supine and standing systolic blood pressure
 - ≥ 160 mmHg
 - < 100 mmHg
 - ≥ 20 mmHg increase from baseline
 - ≥ 20 mmHg decrease from baseline
 - ≥ 40 mmHg increase from baseline
 - ≥ 40 mmHg decrease from baseline
- Supine and standing diastolic blood pressure
 - ≥ 100 mmHg
 - < 50 mmHg
 - ≥ 10 mmHg increase from baseline
 - ≥ 10 mmHg decrease from baseline
 - ≥ 20 mmHg increase from baseline
 - ≥ 20 mmHg decrease from baseline
- Supine and Standing Pulse rate
 - ≥ 120 bpm
 - < 48 bpm
 - ≥ 30 bpm increase from baseline
 - ≥ 30 bpm decrease from baseline
- Orthostatic change ≥ 20 mmHg increase from baseline for systolic blood pressure and diastolic blood pressure
- Orthostatic change ≥ 20 mmHg decrease from baseline for systolic blood pressure and diastolic blood pressure

For Weeks 2, 6, 12, 24, 36, and 52 plots of the mean change from baseline at each timepoint will be displayed for blood pressure and pulse rate in supine and standing position and orthostatic change.

All vital sign data collected will be included in the data listings.

9.8.5. Body Weight

Body weight will be summarized at Weeks 12, 24, 52, early termination and safety follow-up visits.

Summary tabulations of weight (n, mean, standard deviation, median, minimum, and maximum) at each scheduled visits, and change from baseline will be provided.

All body weight data collected will be included in the data listings.

9.8.6. Columbia-Suicide Severity Rating Scale

The number and percent of subjects reporting "Yes" for each of the 5 questions to suicidal ideation and 6 questions about suicidal behavior will be summarized. In addition, for suicidal behavior, the total number of actual attempts, total number of interrupted attempts and total number of aborted attempts will be summarized (n, mean, standard deviation, median, minimum and maximum) by visit.

All C-SSRS data collected will be included in the data listings.

9.8.7. Modified Minnesota Impulsive Disorders Interview

mMIDI is reported at Weeks 2, 6, 12, 24, 36, 52, early termination and safety follow-up. For the mMIDI module scores and total score, if a question is not answered with a module, then that given module score and the total score will not be determined for the subject at the visit.

The mMIDI modules are Buying Disorder, Compulsive Gambling, Compulsive Sexual Behavior, Compulsive Eating, and Punding Behavior. The number and percent of subjects in each module with a positive/negative indication for the module will be reported. In addition, shift from baseline to each scheduled visit will be summarized.

All mMIDI data collected will be included in the data listings.

9.8.8. Epworth Sleepiness Scale and Assessment of Sudden Episodes of Sleep

Epworth Sleepiness Scale (ESS) is reported at Weeks 2, 6, 12, 24, 36, 52, early termination and safety follow-up, collected during patient's ON state. Daytime sleepiness as measured by the ESS, including assessment of episodes of sudden onset of sleep. ESS will be summarized by visit. Assessment of sudden episodes of sleep will be analyzed similarly.

All ESS data collected will be included in the data listings.

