2.1.2 Secondary Objectives

The secondary objectives of this study are to evaluate the effects of tozadenant on the occurrence of daytime drowsiness, impulsive behavior, and suicidality.

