9.4.3 Epworth Sleepiness Scale (ESS)

The ESS is a copyrighted short self-administered assessment that measures daytime sleepiness. The instrument asks patients to rate the probability of dozing in eight different day-to-day scenarios. The ratings are as follows:

0 = no chance of dozing

1 = slight chance of dozing

2 = moderate chance of dozing

3 = high chance of dozing

The scores for the eight situations are then added to one total score. A score within the range 0–9 is considered to be normal while a score within the range of 10–24 would indicate medical help should be solicited.

An example of the ESS is provided in [Appendix 15.2](#).

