2.2. Secondary Objectives

To evaluate the effects of tozadenant on the occurrence of daytime drowsiness, impulsive behavior, and suicidality.

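### The secondary objective is occurrence, but the SAP plans no any-time or new-onset patient count for ESS, mMIDI or C-SSRS

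*SAP*

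**What the plan says.** Protocol 2.1.2 sets the secondary objectives as to "evaluate the effects of tozadenant on the occurrence of daytime drowsiness, impulsive behavior, and suicidality"; SAP 2.2 repeats them. The planned summaries are as follows.

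- **Drowsiness (SAP 9.8.8).** "ESS will be summarized by visit", with no score category. Protocol 9.4.3 treats 0–9 as normal and says that a score of 10–24 "would indicate medical help should be solicited".
- **Sudden onset of sleep (SAP 9.8.8).** "Assessment of sudden episodes of sleep will be analyzed similarly", which reads as by visit. Under Protocol Appendix 15.3, the question after Screening covers only the time since the previous visit. A Yes answer that is a change from Screening is to be reported as an adverse event.
- **Impulsive behavior (SAP 9.8.7).** "The number and percent of subjects in each module with a positive/negative indication for the module will be reported". No period is given. A shift from baseline to each scheduled visit is added.
- **Suicidality (SAP 9.8.6).** The number and percent answering Yes are given "for each of the 5 questions to suicidal ideation and 6 questions about suicidal behavior will be summarized". No period is given. Only the attempt counts in the next sentence are tied to visits.

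Elsewhere the SAP does summarize over the whole study. SAP 9.8.3 has a shift to the worst post-baseline laboratory value, SAP 9.8.9 has categories of the maximum post-dose QT/QTcF, and SAP 9.8.1 counts each patient once per SOC or PT for TEAEs.

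**The concern.** In a single-arm descriptive study, the natural measure of occurrence is the number of patients who had the event at any time on treatment, and how many of them did not have it beforehand. The instruments chosen for the secondary objective do not get that measure, while laboratory values and QTcF do.

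A reader of the study report would have a series of by-visit figures and could not tell whether, say, nine positives at each visit were the same nine patients throughout or a different nine each time. For ESS, by-visit score summaries would not show how many patients moved from the normal to the abnormal range. For C-SSRS and mMIDI, the percentages could be programmed by visit, over all post-dose visits, or with Screening and Baseline answers included, because the text does not choose.

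**Working it through.** **Figures in the plan.** The plan gives no expected rate and no stated figure on this point, so there is none to reproduce. The inputs from the documents are k = 6 on-treatment visits (Weeks 2, 6, 12, 24, 36 and 52) and about N = 450 enrolled. The per-visit proportion p is an assumption.

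**Bounds.** With complete data and a constant p, there are k × p × N positive results in all. Each affected patient contributes between 1 and k of them. Hence

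- lowest any-time incidence (the same patients at every visit): p
- highest (different patients at every visit): min(1, k × p)
- independent visits: 1 − (1 − p)^k

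| Assumed p | Lowest | Independent visits | Highest | Patients of 450, lowest to highest |
|---|---|---|---|---|
| 1% | 1% | 1 − 0.99^6 = 5.9% | 6% | 4.5 to 27 |
| 2% | 2% | 1 − 0.98^6 = 11.4% | 12% | 9 to 54 |
| 3% | 3% | 1 − 0.97^6 = 16.7% | 18% | 13.5 to 81 |

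The same by-visit table is thus compatible with a six-fold range. The independent case lies close to the top of it. A persistent condition would lie near the bottom.

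**New onset.** These bounds are for any positive result. New-onset incidence also needs a split by status before treatment. The mMIDI shift table has that split, but only one visit at a time. For ESS nothing comparable is planned.

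**Which assessments reach a table.** SAP 9 puts early-termination data into a scheduled week if the visit falls in that window, and otherwise into a separate column; each value is used once. Those results are kept, but in a different place from the patient's other visits. Protocol 6.2.21.2 allows C-SSRS and mMIDI at unscheduled visits. The visit list in SAP 9.8.7 does not include these, so a positive mMIDI module found there might appear only in a listing.

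**What the TEAE tables cover.** SAP 5.12 defines TEAEs from first dose through Safety Follow-up, and SAP 9.8.1 counts patients once per SOC or PT. With the reporting rule in Appendix 15.3, this gives an over-study patient count for new sudden onset of sleep, subject to the investigator's judgment that it is a change from Screening. The protocol has no matching rule that makes an ESS of 10 or more, a positive mMIDI module or a C-SSRS Yes an adverse event.

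**The case against.** The strongest reply has four parts.

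1. **The SAP is not confined to by-visit tables.** The main C-SSRS and mMIDI sentences carry no visit qualifier. This stands. A reader might infer that everything is by visit only, but that is literal only for ESS, sudden sleep, C-SSRS attempt counts and the mMIDI shift. For the other two percentages, the fault is an unstated period.

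2. **TEAE tables already give patient-level incidence.** This stands for new sudden onset of sleep, so it would be wrong to say that no planned table counts those patients. It also holds for any other sleepiness, impulse-control or suicidality event that is reported as an AE. Protocol 9.1.2 asks investigators to review the self-assessments, but that does not turn a positive score into an AE, so coverage of the other instruments is incomplete.

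3. **Entry and withdrawal rules limit the problem.** Recent C-SSRS Question 4 or 5 ideation excludes a patient, and so does a positive mMIDI module unless a structured interview rules out a disorder (Protocol 4.2). A post-baseline Question 4 or 5 Yes leads to withdrawal (Protocol 4.3.2). For that C-SSRS item, most positives would be new and by-visit counts would nearly add up to patients. This is fair. It does not carry over to ESS, and only partly to mMIDI, where enrolled patients can have a positive module at Screening and a positive result later leads to a discussion rather than automatic withdrawal.

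4. **The study is descriptive, and 10–24 is a score interpretation rather than an endpoint.** Both are true. They keep the point to a reporting gap. They do not supply the count that the objective asks for, and listings are not a summary.

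A reader might also infer that by-visit percentages will fall as affected patients leave. That is possible, but nothing in the documents shows it, and early-termination results are retained.

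**Conclusion.** The gap is real but limited. The SAP prespecifies no any-time post-baseline or new-onset patient count for ESS, mMIDI or C-SSRS. It is clearest for ESS, which is by visit with no category. For mMIDI and C-SSRS it lies in the unstated period and the missing over-study summary. Sudden onset of sleep is partly covered by the TEAE table.

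To say that the secondary objective goes unanswered would be too strong: by-visit counts, shifts, TEAE tables and listings all bear on it. The narrower conclusion is that patient-level occurrence on these instruments cannot be read from the planned tables. The possible discrepancy is a factor of 1 to 6, assuming a constant per-visit proportion, six visits and complete data. Where in that range the study would fall cannot be known from the documents. No hypothesis test is planned, so no error rate or power is affected.

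**What to change.** Keep the by-visit tables and add one Safety Set table of n (%) over all assessments after first dose. Include early-termination and safety follow-up visits, and unscheduled visits where the instrument was given. The rows would be:

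- ESS 10–24, among patients scoring 0–9 at baseline
- any sudden-sleep Yes, overall and among patients answering No at Screening
- at least one positive mMIDI module, among patients with none at Screening (mMIDI is not scheduled at Baseline)
- C-SSRS ideation Question 4 or 5, or any suicidal behavior

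The protocol already defines each category: the ESS split in 9.4.3, the positive module in Appendix 15.4, the C-SSRS items in 4.3.2 and the sudden-sleep answers in Appendix 15.3. State in SAP 9.8.6 and 9.8.7 that the percentages refer to assessments after first dose.

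The cost is one extra descriptive table from data already collected.

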9.8.9. ECG

ECG data will be summarized for the following visits: Weeks 2, 6, 12, 24, 36, 52, early termination and safety follow-up. Descriptive statistics (n, mean, standard deviation, median, minimum and maximum) of each parameter (HR, PR, RR, QRS, QT, and QTcF) will be displayed for the observed value and change from baseline at each scheduled listed above.

The number and percentage of subjects with maximum post-dose QT/QTcF interval within the following ranges will be summarized:

- ≤ 450 msec
- > 450 msec and ≤ 480 msec
- > 480 msec and ≤ 500 msec
- > 500 msec.

In addition the number and percentage of subjects with maximum change from Baseline in QT/QTcF interval within the following ranges will be summarized:

- ≤30 msec
- >30 msec
- ≤60 msec, and >60 msec.

ECG findings will be classified as normal or abnormal, with abnormal values further classified according to clinical significance (yes/no). The percentage of subjects with clinically significant findings and clinically significant treatment-emergent findings will be summarized for each visit.

All ECG data collected will be included in the data listings.

9.8.10. Physical and Neurological Examinations

Physical and neurological examinations are performed at Weeks 12, 32, 36, 52, early termination and safety follow-up visits. The number and percentage of subjects with normal/abnormal findings will be summarized by body system/neurological area and visit.

All abnormalities reported will be included in the data listings.

10. VALIDATION

- 100% of unique tables will be independently programmed by a second programmer for numeric results. Statisticians will be involved in the process of programming and validating tables.
- Figures will be checked for consistency against the corresponding tables and listings.
- Listings will be checked for consistency against corresponding tables, figures, and derived datasets.

The entire set of TFL will be checked for completeness and consistency.

11. PROGRAMMING SPECIFICATIONS

11.1. Format of Appendix Tables/Figures/Listings

1. Unless otherwise specified, all computer-generated tables, figures and listings (TFL) should be produced (via SAS® ODS) into RTF output, which can be imported in table format via Microsoft® Word. The TFLs should be in landscape mode with required margins: at least 1.5 inches on top (the binding margin, or left for portrait output), at least 1 inch on right, left, and bottom. All output should have the following headers on each page:
 - “CONFIDENTIAL” header in the upper center:
 - Two-line header at the upper left margin:

ACORDA THERAPEUTICS, INC.

PROTOCOL No.: *TOZ-CL06*

- Header with a date (time and date output was automatically generated via SAS) and page number at the upper right margin:

DATE: &SYSTIME &SYSDATE
PAGE: X of N

TFLs should be internally paginated in relation to total length (i.e., page number should appear sequentially as page X of N, where N is the total number of pages within a table or listing).

2. Each TFL should be identified by in a sequential numeric order, and the TFL designation (e.g., Table 1) should be centered above the title. A decimal system within the numeric numbering (i.e., x.y and x.y.z) should be used to identify TFLs with related contents. The title is centered in initial capital characters and should include the population type analyzed (e.g. Safety Population). The title and designation are single-spaced, but are separated from the TFL by at least a double space.

Table No.

First Line of Title
Second Line of Title (if needed)
Population Type Analyzed

3. Column headings for tables and listings should be in initial upper-case characters.
4. For variables with numeric values, include “unit” in column heading when appropriate.
5. Footnotes should be single spaced, but separated by at least a double space from the bottom line of the TFL. The notes are left justified, with each note starting on a new line. Avoid numeric references, which can be confused with data; rather use asterisks and other non-numeric symbols to refer to footnotes. Patient-specific footnotes should be avoided. The source data set name (and for tables and figures the source listing number) as well as the source SAS program names and locations (with reduced font if necessary) should be displayed as the last footnotes in each TFL. For example the set of footnotes for a table:
*: Footnote 1
**: Footnote 2
Note: Footnote 3
Source Listing: Listing *X* (*data set name*)
SOURCE PROGRAM: path\filename
6. All data listings should be sorted by investigator site, patient within investigator site, and study visit date/time within patient where appropriate.
7. For tables that summarize categorical (discrete) data, all categories between the maximum and minimum category should be presented in the table, even if there is zero

entry for a particular category. An Unknown or Missing category should be added to any variables to indicate missing information, if appropriate

Severity Rating	n
Severe	0
Moderate	8
Mild	3
Missing	2

8. If the categories are not ordered (e.g., Medical History, Reasons for Discontinuation from the Study, etc.), then only those categories for which there is at least 1 patient represented in 1 or more groups should be included.
9. Unless specified otherwise, tabular display of data for medical history, prior / concomitant medications, and all tabular displays of adverse event data should be presented by the body system, drug class, or SOC with the highest occurrence in decreasing order. Within the body system, drug class and SOC, medical history (by preferred term), drugs (by ATC1 code), and adverse events (by preferred term) should be displayed in decreasing order. If incidence for more than 1 term is identical, they should then be sorted alphabetically. Specifically, prior and concomitant medications other than Anti-Parkinson's medications should be displayed by therapeutic class and preferred term. Prior and concomitant Anti-Parkinson's medications should be displayed by therapeutic class, chemical/therapeutic/pharmacological subgroup, and preferred term.
10. Unless otherwise specified, the estimated mean and median for a set of values should be printed out to one more decimal place than the original values and rounded appropriately. Standard errors (or standard deviations) should be printed out to two additional decimal places than the original values and rounded appropriately. The range should report the same as the original values. For example, for age (with original value in whole years):

N	xx
Mean	xx.x
S.E.	xx.xx
Median	xx.x
Range	xx-yy

11. All fractional numeric values should be printed with a zero to the left of the decimal point (e.g., 0.12, 0.3).
12. Unless otherwise specified, percentage values should be printed with one digit to the right of the decimal point (e.g., 12.8%, 5.4%). While count and percentage values are presented together, percentage values should be printed in parentheses 1 space after the count (e.g., 7 (12.8%), 13 (5.4%)). Any counts of 0 will be presented as 0 and not as 0 (0%). Unless otherwise noted, for all percentages, the number of patients in the analysis set for the cohort who have an observation will be the denominator.
13. Missing descriptive statistics due to non-estimability in tables, as well as missing data in patient listings should be represented as either a hyphen (“-“) with a corresponding

footnote (“ - = unknown or not evaluated”), or as “N/A” with the footnote “N/A = not applicable” whichever is appropriate.

14. Dates printed as a result in the TFL should be printed in SAS DATE9. format (“DDMONYYYY”: 01 Jul 2002). Missing portions of dates should be represented on patient listings as dashes (e.g., -- Jul 99). Dates that are missing because they are not applicable for the patient should be listed as “N/A”, unless otherwise specified.
15. All observed time values should be presented using a 24-hour clock HH:MM:SS format (e.g., 01:35:45, or 11:26).
16. Data in columns of a table should be formatted as follows:
 - Alphanumeric values are left-justified;
 - Whole numbers (e.g., counts) are right-justified; and
 - Numbers containing fractional portions are decimal aligned

APPENDIX 1 GLOSSARY OF ABBREVIATIONS

ADaM	Analysis Dataset Model
ADL	Activity of Daily Living
AE	Adverse Event
BMI	Body Mass Index
BID	Twice a Day
CDISC	Clinical Data Interchange Standards Consortium
CGI-S	Clinical Global Impression-Severity
CGI-I	Clinical Global Impression-Improvement
C-SSRS	Columbia-Suicide Severity Rating Scale
eCRF	Electronic Case Report Form
ECG	Electrocardiogram
ESS	Epworth Sleepiness Scale
FAS	Full Analysis Set
LLQ	Lower Level of Quantitation
MedDRA	Medical Dictionary for Regulatory Activities
mMIDI	Modified Minnesota Impulsive Disorders Interview
mFAS	Modified Full Analysis Set
PD	Parkinson's Disease
PDQ-39	Parkinson's Disease Questionnaire
PGI-I	Patient Global Impression-Improvement
PK	Pharmacokinetics
PT	Preferred Term
SAP	Statistical Analysis Plan
SAE	Serious Adverse Event
SD	Standard Deviation
SDTM	Study Data Tabulation Model
SOC	System Organ Class
SS	Safety Set
TEAE	Treatment Emergent Adverse Event
TFL	Table, Figures and Listings
UPDRS	Unified Parkinson's Disease Rating Scale
WHODRUG	World Health Organization Drug Dictionary

